We propose to obtain consent from a total of 200 participants in order to identify 48 who meet all inclusion and exclusion criteria and complete all aspects of the study. During a phone screening interview, the study will be described in detail and preliminary participant characteristics (e.g. age, number of cigarettes per day) will be assessed. Those participants who meet criteria for participation will be invited to our offices for an informed consent and screening visit.

Screening session. During screening, all aspects of the study will be described to subjects and informed consent will be acquired. Breath and saliva samples will be collected in order to verify smoking status and blood alcohol level (BAL); and measures including, but not limited to, smoking

history, nicotine dependence, and mood will be collected. Vitals such as heart rate, blood pressure and weight/height will also be measured. Urine samples will be obtained in order to screen for illicit drug use and pregnancy status. Use of illegal drugs will be exclusionary. Marijuana use will not be exclusionary, but participants must agree to not use marijuana 24 hours prior to sessions and may not mix their marijuana with tobacco (i.e. blunts). Females who test positive for pregnancy will be excluded from the study and be given options for smoking cessation programs. Participants will also be interviewed regarding their smoking behavior including an assessment of contexts (places) in which they smoke and abstain from smoking cigarettes.

Inclusion criteria:

- 1) generally healthy [(i.e. ambulatory, not currently sick)]
- 2) between the ages of 18 and 65
- 3) smoking of at least 5 cig/day of a brand delivering ≥ 0.5 mg nicotine (FTC method) for ≥ 1 year
- 4) an expired CO concentration of at least 10 ppm (to confirm inhalation) or urinary cotinine >1000 ng/mL (NicAlert = 6).
- 5) interest in quitting smoking within the timeframe of the experiment.
- 6) ability to identify 4 personal smoking and 4 personal non-smoking places.
- 7) right handed as measured by a three-item scale used in our laboratory
- 8) own a smartphone
- 9) Breath Alcohol Level =0.000

Exclusion criteria:

- 1) immediate or no desire to quit smoking;
- 2) inability to attend all required experimental sessions;
- 3) use of other tobacco products or e-cigarettes more than 9 days in the past 30 days;
- 4) current alcohol or drug abuse;

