Participants will wear Nicotine patches (Nicoderm CQ®): 21mg/day patches for 6 weeks, then step down to 14mg/d patches for 2 weeks and finally step down 7mg/d for the last 2 weeks of study protocol. If the participant smokes less than 10 cigarettes/day, we will start them on 14mg/day patches for 6 weeks before stepping down to 7mg/day patches for the final 4 weeks of treatment. Insomnia and abnormal dreams are common and expected side effects associated with 24 hour nicotine patches. If a subject complains of disturbed sleep, he or she will be instructed to remove the patch at bedtime and apply a new one the next day at the usual time. Skin irritation may occur, although this will be minimized by changing the site of patch application daily. Using 1% hydrocortisone cream on the affected area will be recommended to help reduce skin irritation. If a subject develops itching or a rash at the patch site, he or she will be advised to use 1% hydrocortisone cream on the affected area. Symptoms associated with nicotine toxicity include lightheadedness, dizziness, nausea, fainting and vomiting. Symptoms considered moderate to severe in nature will be evaluated by the study medical staff by telephone or in person, depending upon the level of severity. Upon evaluation, the subject will then be given the choice of continuing in the study while discontinuing patch use.

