Lab Visits: Four lab visits will be conducted during the 10 weeks following the quit day. The visits will take place 1 week, 2 weeks, 6 weeks and 10 weeks post quit day. Each visit will have a window period of +/- 3 days from targeted date, calculated from date of camera return visit. Visits exceeding the window period will be recorded as a protocol deviation. These visits will be largely identical except that instructions and reminders to participants about upcoming events will vary from session to session. At each lab visit the following will be collected: vitals (heart rate, blood pressure and weight), breath CO and measures of smoking withdrawal and mood. Nicotine patches and instructions for using them will

be provided at each session. Advice on quitting and minimal support will be provided as requested at these visits. During the third lab visit participants will review and annotate their GPS tracks with study staff by indicating the name (e.g. home, work, library) of stay-points (i.e. places they spent more than 1 hour). Each lab visit will require 20-30 minutes of participant time.

6 month Follow-Up phone call. Participants will be contacted by phone 6 months after completing the study to complete a brief interview about current smoking status and nicotine dependence.

DATA ANALYSIS

The primary aim of the study is to examine differences in brain responses to personal vs. standard smoking and non-smoking environments. Multiple methods will be used to test hypotheses about brain functioning during cue-reactivity (CR): a region of interest (ROI) based approach for testing specific *a priori* hypotheses and a voxel-wise whole-brain analysis for identifying unexpected findings. This two-pronged approach to fMRI data analysis will allow us to maximally evaluate variability in signal over space and time while minimizing the risk of both Type I and II error. For each hypothesis, the brain CR variable of interest will be the difference in mean % signal change. We will examine correlation between brain responses to smoking environments (minus non-smoking environments) and smoking cessation outcomes (i.e. days to lapse, days to relapse).

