Women of childbearing potential: Pregnant or nursing women will be excluded from the study. Female participants will undergo a urine pregnancy test at screening. Subjects must also agree to use appropriate contraception during the course of the trial. Medically acceptable contraceptives include: (1) surgical sterilization (such as a tubal ligation or hysterectomy), (2) approved hormonal contraceptives (such as birth control pills, patches, implants or injections), (3) barrier methods (such as a condom or diaphragm) used with a spermicide, or (4) an intrauterine device (IUD). Women who smoke and are over the age of 35 should not take oral contraceptives that contain estrogen without consulting their physician. Smoking while using oral contraceptives can increase the risk of having a cardiovascular

event such as a heart attack or stroke. Additionally, there is a potential risk of thrombosis associated with hormonal therapy (including contraceptives) and smoking. They will be encouraged in the consent form to notify study staff if they believe a change in their pregnancy status has occurred during the trial.

Management of side effects: Reports of side effects will be obtained by study staff and communicated to the principle investigator and study physician, who will determine the most appropriate course of action, which may include options for termination of study participation. Participants will be reminded of their option to withdraw from the study at any time. If a participant decides to withdraw from the study, we will ask them to return for a final visit to return all study materials. In the event of significant side effects it will be necessary to reduce patch dosage. In response to complaints of insomnia, instructions will be given to remove skin patches at bedtime. In the event of other intolerable side effects patches will be discontinued completely.

MRI: MRI provides clinically relevant anatomic and functional information non-invasively and with minimal risk, if the well-known contraindications (such as pacemakers) and potential hazards (such as attraction of metallic objects) are avoided.

Do you feel that there is any risk to wearing the GPS tracker and having their whereabouts known? I recognize that smart phones and activity trackers have this feature, but you are specifically providing them with a GPS tracker for tracking purposes for the study.

PARTICIPANT RECRUITMENT AND COMPENSATION

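### The correlation of brain response with days to lapse and relapse names no covariate, although baseline smoking rate may relate to both and also sets the patch course; patch use is not stated as recorded

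*Combined protocol and SAP*

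**What the plan says.** The cessation analysis is one sentence in DATA ANALYSIS: "We will examine correlation between brain responses to smoking environments (minus non-smoking environments) and smoking cessation outcomes (i.e. days to lapse, days to relapse". Neither that section nor any other names a covariate, a stratification or a way of handling patch changes.

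The inclusion criteria admit "smoking of at least 5 cig/day of a brand delivering" at least a stated nicotine yield. Under Nicotine Patches, the general course is "21mg/day patches for 6 weeks, then step down to 14mg/d patches for 2 weeks", then 7 mg/day for the last 2 weeks. The exception is "If the participant smokes less than 10 cigarettes/day, we will start them on 14mg/day patches for 6 weeks", followed by 7 mg/day for 4 weeks. Smoking rate is known at entry: in the phone interview, "preliminary participant characteristics (e.g. age, number of cigarettes per day) will be assessed".

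The course can change later. Nicotine Patches allows bedtime removal, and allows a participant to stop patches while staying in the study. RISK/BENEFIT ASSESSMENT (Management of side effects) adds dose reduction and states: "In the event of other intolerable side effects patches will be discontinued completely".

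Under Lab Visits the data list reads: "At each lab visit the following will be collected: vitals (heart rate, blood pressure and weight), breath CO and measures of smoking withdrawal and mood". Patches are handed out at these visits, but no wear, count or return record is described.

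**The concern.** Smoking rate is a common antecedent. It precedes the scan and the quit attempt, it may relate to cue reactivity and to how soon a person lapses, and it fixes which patch course the person receives. A correlation between brain response and days to lapse can then arise partly because heavier and lighter smokers differ on both. If the result is read as evidence about reactivity to smoking environments, that reading is not secured by an analysis that leaves smoking rate out. Because no model is fixed, covariates could also be chosen after the results are seen.

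The second part concerns description. Without a stated record of patch use, the report may be unable to say how much treatment participants took, or whether a given lapse happened on or off the patch. If this is not recorded at the time, it may not be recoverable later.

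**Working it through.** The plan gives no power, alpha, effect size or correlation for this analysis, so there is no figure of its own to reproduce. Its target is 48 completers: "We propose to obtain consent from a total of 200 participants in order to identify 48 who meet all inclusion and exclusion criteria".

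**1. Can both courses occur?** Entry starts at 5 cigarettes/day and the split is at 10, so smokers of 5 to 9 per day are eligible and would take the lower course. How many of the 48 that would be is not stated.

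**2. Labelled dose over 10 weeks.**
- General course: 21×42 + 14×14 + 7×14 = 882 + 196 + 98 = 1,176 mg.
- Under 10 cigarettes/day: 14×42 + 7×28 = 588 + 196 = 784 mg.
- Difference: 392/1,176 = one third.

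**3. Illustration of the induced correlation.** Assumptions, none from the documents except n=48:
- two-sided alpha 5% and linear-normal variables;
- smoking rate and patch course treated as one variable that correlates r with brain response and r with outcome;
- no link between the two once that variable is held fixed.

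The marginal correlation is then r×r. By Fisher's z, the shift is atanh(r²)×√(48−3), with √45 = 6.708, and the rejection probability is 1 − Φ(1.96 − shift) + Φ(−1.96 − shift). The simulation columns use 20,000 trials per row.

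| r | r² | shift | rejects, Fisher z | rejects, simulated | adjusted, simulated |
|---|---|---|---|---|---|
| 0.2 | 0.04 | 0.268 | 5.8% | 5.9% | 5.2% |
| 0.3 | 0.09 | 0.605 | 9.3% | 9.3% | 5.1% |
| 0.4 | 0.16 | 1.083 | 19.1% | 19.2% | 5.0% |
| 0.5 | 0.25 | 1.713 | 40.3% | 40.7% | 5.1% |

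**4. Sensitivity to direction.** Heavier smokers get the higher-dose course. Suppose heavier smoking shortens time to lapse and the higher course lengthens it, with equal and opposing coefficients, and course is a step in smoking rate. Simulated at n=48 with 5,000 trials per setting, the unadjusted test rejects in about 5% at 0.3, 6% to 7% at 0.4 and 7% at 0.5.

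**5. Price of adjusting.** The correlation detectable with 80% power is tanh((1.960 + 0.842)/√45) = 0.395 unadjusted, and tanh((1.960 + 0.842)/√44) = 0.399 with one covariate.

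**6. What is recorded.** Baseline smoking rate is collected, so the assigned course can be derived. Patch strength and days worn appear in no data list. Side-effect reports reach the investigator and study physician and would show some reductions and stops. The app's item list is open-ended but does not name patch use.

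**The case against.** The strongest reply is that the plan promises only a correlation and makes no causal claim. In the illustration the marginal correlation really is r², so a test that rejects zero is right about that quantity. For predicting lapse, the unadjusted correlation is a legitimate target. This stands: the percentages are not false-positive rates of the analysis as stated. They bear only on a claim that the association is specific to environment reactivity.

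It also stands that the strengths are assumed, that 0.2 to 0.3 gives little more than 5%, and that opposing effects nearly remove the excess. The adjusted column stays near 5% by construction, for a perfectly measured linear-normal confounder; days to lapse need not behave that way.

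A further objection is over-adjustment: the plan treats the amount smoked in a place as a source of brain reactivity, so removing cigarettes/day might remove part of the construct. This does not defeat the point. Baseline smoking rate precedes both scan and outcome, total rate is not the same as location-specific intensity, and both results can be shown.

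A reader might infer that later patch reductions and stops also confound the brain measure. They do not: there is one scan, and what happens after it cannot affect it. A reader might also infer that the dose taken cannot be reconstructed at all. The documents do not support that either, since staff handle side-effect reports and the app items are not fully listed. The supportable statement is that patch use is not stated as collected.

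**Conclusion.** The point holds in a limited form. The brain-outcome correlation may partly reflect heaviness of smoking and the patch course tied to it. By how much is unknown, because the documents give no confounder strength. The illustrative 6% to 41% requires correlations of 0.2 to 0.5 with both variables and no cancelling effect of patch course; with opposing effects it falls to about 5% to 7%.

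Three stronger readings should be avoided. The plan does not rule out adjustment; it is silent. Eligibility shows that both patch courses can occur, not that each will hold a meaningful share of the 48. And the aim that DATA ANALYSIS calls primary, the contrast of personal with standard environments, does not involve cessation outcomes and is unaffected.

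The patch-use gap is one of description and interpretation, not of confounding.

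**What to change.** In DATA ANALYSIS, state in advance that the association of brain response with days to lapse and relapse will be reported both unadjusted and adjusted for baseline cigarettes/day, and that any claim specific to environment reactivity will rest on the adjusted result. Use this one covariate; the patch course is a function of it, and adding course as well would bring collinearity.

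Add one item to the existing lab-visit form: patch strength worn, days worn since the last visit, and the date and reason of any reduction or stop. Use it to describe exposure and to show whether each lapse occurred on or off the patch. Do not exclude participants or censor follow-up at patch discontinuation: stopping may follow a lapse, and the censoring would then be informative.

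The cost is one degree of freedom (detectable correlation 0.399 instead of 0.395) and about a minute per visit, with no extra visits. No dose or stopping rule is changed or judged.
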